## JHM IRB - eForm A – Protocol

### 1. Abstract

Hepatitis C virus (HCV) is a leading cause of liver cancer and HCV-related liver disease is among the most common causes of non-AIDS related death among people living with HIV (PLWH). One quarter of PLWH in the U.S. are co-infected with HCV, which leads to a 3-fold increase in progression to end stage liver disease and hepatocellular carcinoma. HCV can be cured, but less than half of PLWH with chronic HCV in the U.S. have linked to HCV care, and about 7% initiated treatment. Poor treatment initiation rates historically have been due to low efficacy among PLWH, but HCV care now is at a turning point. We have the ability to substantially decrease HCV-related morbidity and mortality in PLWH with the availability of effective all-oral treatment. As patients are funneled into HCV care, improving the process of linking to care and treatment preparation related to HIV medication modifications necessary for current HCV regimens is essential to maximize the lifesaving potential of available therapies among PLWH.

There are several barriers to linkage to HCV care and treatment. HCV is a “silent epidemic” often presenting no symptoms for 20 years. Thus, perceived need for treatment is low among persons infected with HCV. Knowledge about HCV and its available therapies is also low and lags behind new advancements in HCV treatment. For PLWH who are linked to HCV care, drug interactions between new HCV therapies and HIV treatment regimens introduce a new barrier to HCV treatment initiation. Up to 88% of PLWH will need to switch their HIV treatment regimen to avoid contraindicated drug interactions. The April 8, 2015 updated Guidelines for the Use of Antiretroviral Agents in HIV-1-infected Adults and Adolescents emphasize the need to modify HIV regimens to treat HCV in many PLWH. But modifying HIV treatment regimens can have severe negative consequences, including decreased quality of life, increased symptom burden, and loss of viral suppression. New approaches to modifying HIV treatment regimens are now crucial to smooth the transition into initiating HCV therapy for PLWH.

In similar settings and populations, nurse case management interventions have been shown to improve these outcomes. However, few of these interventions have been rigorously tested in the context of HCV. Evidence supports combining existing intervention components from similar populations to improve HCV care. Strengths-based education, patient navigation, and reminder systems improve knowledge and adherence to appointments. The addition of novel nurse-initiated referral and HIV/HCV drug interaction coordination has never been tested, but may further improve knowledge and motivation to engage in care and address this important barrier for PLWH. Therefore, it is hypothesized that nurse case management consisting of nurse-initiated HCV referral, strengths-based HCV education, patient navigation, appointment reminders, and care coordination for HIV treatment modifications will improve linkage to HCV care and treatment initiation among PLWH.

### 2. Objectives

The specific aims of the proposed RCT are to:

1. Test whether a nurse case management intervention will **increase linkage** of persons with HIV/HCV co-infection to an HCV treatment pathway via the Viral Hepatitis Center compared to enhanced usual care  
*H0:* A higher proportion of those who are randomized to the intervention arm will attend the Viral Hepatitis Clinic or enroll in an HCV-treating clinical trial within 60 days of randomization compared to those who receive enhanced usual care.
2. Determine if a nurse case management intervention will **decrease time to HCV treatment initiation** among persons with HIV/HCV co-infection compared to enhanced usual care

Date: May 8, 2017

Principal Investigator: [name], MPH, NP

Application Number: IRB00081068

*H0:* Those who are randomized to the intervention arm will have a decreased time to HCV treatment initiation from the point of randomization compared to those who receive enhanced usual care.

3. Describe the characteristics associated with uptake of HCV care among PLWH, controlling for covariates.

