## **Enrollment**

**Patient Population/Setting:** The Bartlett Specialty Practice (formerly the Moore Clinic for HIV Care) at the Johns Hopkins Hospital provides HIV primary care to approximately 3500 men and women over the age of 18 per year. The clinic serves a primarily adult, urban population, with approximately 80% of patients being African American. The average age of clinic patients is 49 years. Approximately 50% of patients with HIV are co-infected with HCV. In Maryland, HCV therapy currently must be managed by a hepatology, gastroenterology, or infectious disease specialist for Medicaid reimbursement. The Viral Hepatitis Specialty Clinic, staffed with hepatologists and hepatitis-focused infectious disease physicians and nurse practitioners, is located within the Bartlett Specialty Practice. As of May 2015, 480 HIV/HCV co-infected patients at the Moore Clinic had *never* attended an appointment at the Viral Hepatitis Clinic; 90 patients never went to their scheduled appointments and 390 patients had never been scheduled for HCV care. In addition, a number of patients have not attended an appointment at the Viral Hepatitis Clinic in the era of all-oral therapy (including the past year). The median time between referral and available new patient appointment at the Viral Hepatitis Clinic is one week.

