with scores of 20 or greater (severe) will be referred to their primary provider, or, if the primary provider is not available, the covering urgent provider of the day, for further evaluation before the study is continued.

All questions in the protocol will be asked in a private area and can be administered by a study team member in 30-45 minutes. In addition to the subject questionnaire, each instrument contains a section for the research team to interrogate the patient's medical record to verify specific pieces of the medical history. These variables of interest include:

- CD4+ T cell count
- HIV viral load
- Prescribed HIV treatment
- Year of HCV diagnosis
- HCV RNA
- Fibrosis score
- HCV genotype
- HCV referral history
- HCV appointment history
- HCV treatment initiation barriers
- Hopkins appointment no-show rate

In addition to baseline and outcome data collection, monthly activity logs will be collected for each study participant, independent of allocated study arm. The type, quantity, and content of all encounters with a study participant in the Johns Hopkins system will be recorded each month, including nurse visits. This will define usual care for Bartlett Specialty Practice patients. The type, quantity, and content of all Care2Cure study visits will also be recorded to define the dose of the intervention. Data will be collected from the study participant's Epic record and the interventionist's notes.

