**Enhanced Usual Care:** After randomization into the enhanced usual care arm, the nurse case manager will provide participants with the CDC HCV Fact Sheet and phone number for the CFAR Research Study Hotline. Participants will then be referred to the usual clinic appointment check-out process. To check-out of Bartlett Specialty Practice appointments, participants return to the front desk with a paper billing page and printed appointment referrals if applicable. The administrative staff closes the appointment encounter and gives the patient the phone number for the Johns Hopkins Hospital central scheduling phone line to schedule referral-based appointments. Patients are responsible for calling central scheduling to set up the specialty appointment. If an appointment is scheduled, all patients receive an automated appointment reminder call 2 days before the scheduled appointment from Johns Hopkins Hospital. Patients at the Bartlett Specialty Practice have access to nurse case managers and social workers assigned by their primary providers. Participants in the enhanced usual care arm will continue to have usual access to these services. Per the Bartlett Specialty Practice standard care protocol, once a prescription is written for HCV treatment, the assigned nurse case manager will work with the patient to coordinate HCV care; however, HIV nurse case managers are not directly involved in HCV care until after prescription for HCV treatment is written, which is the gap the proposed study seeks to fill.

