Linkage to care will be defined as attendance at one or more appointment within the HCV treatment pathway via the Viral Hepatitis Center, including either traditional clinical care at the Bartlett Specialty Practice or an HCV treatment-providing clinical trial within the Viral Hepatitis Center. This will ensure that participants enrolled in the Care2Cure study have the opportunity to engage in HCV treatment in all pathways offered by the Viral Hepatitis Center and inherent in Johns Hopkins Hospital’s standard of care as an academic institution and research center. Independent of randomization allocation, all study participants will be asked in the baseline characteristic questionnaire if he/she would like to be referred to a clinical trial, with the option to refuse or opt out of trials for non-FDA approved treatments. Based on this participant preference, eligibility for actively recruiting clinical trials at the Viral Hepatitis Center will be assessed. Participants will then be referred by the study nurse case manager to either traditional care at the Bartlett Specialty Practice, a clinical trial with no investigational drug, or a clinical trial with an investigational drug, as eligible and available.

Multiple strengths support this approach to the outcome of linkage to care. In Maryland, patients must have a Metavir score greater than or equal to 2 to receive HCV treatment (Maryland Department of Health and Mental Hygiene, 2015). Linking patients to clinical trials that offer treatment to patients in all stages of liver disease, including F0 and F1, removes this barrier to treatment. This approach also minimizes selection bias. Participants who choose to receive HCV treatment through a trial may be different than those who seek care through the traditional clinical pathway; the Care2Cure study will include both.

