## 7. Study Statistics

### Analysis:

Data will be cleaned and efforts made to minimize the effects of missing data. All provider visits at Johns Hopkins are registered in the electronic medical record, so absence of a registered appointment during the study period will be considered non-attendance for the primary outcome variable. A computer-based data collection method will be used for data collection of independent variables in attempt to minimize missing data. Exploratory and descriptive analysis will be completed for all study variables. Variables will be tested for normality and examined with means and standard deviations or medians and interquartile ranges accordingly. Baseline characteristics comparing the two groups (usual care vs. intervention) will be assessed. Any differences between the groups will be adjusted for in further analysis. The significance level will be set at 0.05. All tests will be two-tailed and analyzed by intention-to-treat.

**Primary Outcome:** The primary outcome is linkage to care, measured by attendance at the Viral Hepatitis Center (either traditional care or an HCV-treating clinical trial) within 60 days of randomization (yes/no). This hypothesis will be tested using a two-sample z-test for the difference in independent proportions comparing the intervention to usual care groups.

**Secondary Outcome:** The secondary outcome is time to HCV treatment initiation, measured by the number of days from randomization to the date HCV treatment is initiated according to the medical record. Kaplan Meier estimates will be conducted to compare time to HCV treatment initiation between participants in the intervention group and the usual care group, and a log-rank test will be used to test the difference. Covariates (age, sex, race/ethnicity, HCV knowledge, substance use, fibrosis score, CD4+ T cell count, HIV viral load, care giving responsibilities, and participation in Cure Club) will be included in the Cox regression model. To account for a time to treatment initiation greater than the observed time period of 6 months, right censoring will be implemented for participants who have not initiated HCV treatment at the end of the 6-month period.

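### Linkage is scored only at the Viral Hepatitis Center, but the Aim 1 hypothesis counts any HCV-treating trial, and trial attendance is confirmed only after a referral

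*Combined protocol and SAP*

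**What the plan says.** The outcome is worded in four places.

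- **Objectives, Aim 1:** linkage "to an HCV treatment pathway via the Viral Hepatitis Center compared to enhanced usual care".
- **Objectives, hypothesis under Aim 1:** a higher proportion of the intervention arm "will attend the Viral Hepatitis Clinic or enroll in an HCV-treating clinical trial within 60 days of randomization". The trial has no site, and the verb is to enrol.
- **Phase 1 – Linking to Care:** at least one attended appointment, where a trial counts if it is "an HCV treatment-providing clinical trial within the Viral Hepatitis Center".
- **Study Statistics, Primary Outcome:** "attendance at the Viral Hepatitis Center (either traditional care or an HCV-treating clinical trial) within 60 days of randomization (yes/no". The Analysis paragraph scores the absence of a registered appointment as non-attendance.

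The Abstract and the opening of Study Procedures describe the goal more broadly, as linkage to HCV care.

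The routes by arm are as follows. In Phase 1 the nurse starts the referral for the intervention arm, calls central scheduling or a trial recruitment number during the visit, and sends reminders for the Center appointment. Under Enhanced Usual Care, controls receive a fact sheet and the "phone number for the CFAR Research Study Hotline". They then go through check-out, where staff "gives the patient the phone number for the Johns Hopkins Hospital central scheduling phone line to schedule referral-based appointments".

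Phase 1 also says that participants in both arms are asked about referral to a trial and, read literally, that the study nurse then refers them. It adds that a trial visit is checked with the trial's coordinator if the participant was referred to a trial.

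Under Data Collection Measures, a log covers both arms: "The type, quantity, and content of all encounters with a study participant in the Johns Hopkins system will be recorded each month". No linkage analysis uses it.

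**The concern.** The outcome is measured at the place to which the intervention directs people. Attendance there can rise because more people enter HCV care, or because people who would have entered care anyway do so at this Center. The primary analysis cannot separate the two, and the broader wording in the Abstract and Study Procedures invites the first reading.

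There is also an ascertainment gap. If the coordinator is contacted only after a referral, a control who reaches a trial through the hotline can be missed, even when that trial is at the Center. This part affects the primary outcome as defined. Care reached elsewhere affects only what the result can be said to mean.

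**Working it through.** **1. The plan's own figure.** Inputs from Sample Size Justification: 0.40 v 0.60, two-sided 0.05, 80% power, 1:1.

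n = [1.96·√(2·0.5·0.5) + 0.8416·√(0.4·0.6 + 0.6·0.4)]² / 0.20² = (1.3859 + 0.5831)² / 0.04 = 96.9, so 97 per group. This matches the plan. Power at 100 per group is 81.2%. The 40% is itself a Viral Hepatitis Clinic attendance rate, so the sample size fits the Center-only outcome.

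**2. Wording side by side.** Aim 1, the Phase 1 definition and the Primary Outcome paragraph agree on the Center. Only the hypothesis sentence leaves the trial's site open, and only it says enrol rather than attend. A participant who enters an HCV-treating trial elsewhere meets the hypothesis and fails the analysed outcome.

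**3. Effect on the planned result if linkage elsewhere were counted.** The share linking elsewhere is not in the documents; the numbers of controls below are assumptions, with none in the intervention arm. Pooled z-test, 100 per arm: z = d / √(2·p̄(1−p̄)/100).

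| Any-site linkage, intervention v control | d | p̄ | z | two-sided p |
|---|---|---|---|---|
| 60 v 40 (none elsewhere) | 0.20 | 0.500 | 2.83 | 0.0047 |
| 60 v 46 (6 controls elsewhere) | 0.14 | 0.530 | 1.98 | 0.047 |
| 60 v 47 (7 controls elsewhere) | 0.13 | 0.535 | 1.84 | 0.065 |

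**4. False-positive rate for a claim about any-site linkage.** Suppose true any-site linkage is equal in the two arms (0.40 to 0.60) and linkage elsewhere scores as failure. The chance of a significant result favouring the intervention is Φ[(d − 1.96·SE₀)/SE₁], with SE₀ pooled and SE₁ unpooled. Two examples at a true rate of 0.50:

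- 5 points of control linkage elsewhere, none in the intervention arm: observed 0.45 v 0.50, (0.05 − 1.96·0.0706)/0.0705 = −1.25, giving 10.5%.
- 10 points v none: observed 0.40 v 0.50, (0.10 − 1.96·0.0704)/0.0700 = −0.54, giving 29.4%.

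Over the whole range of true rates:

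| Linkage elsewhere, control / intervention (points, assumed) | Chance of falsely favouring the intervention |
|---|---|
| 0/0, 5/5 or 10/10 | 2.5% |
| 5/0 | 10.5–10.9% |
| 10/5 | 10.5–11.4% |
| 10/0 | 29–32% |

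In these scenarios the inflation comes from the difference between arms; equal shares leave the rate at 2.5%.

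**5. Power of an any-site analysis.** Starting from 40 v 60 at the Center, adding 5 points in both arms leaves power at 81.6%. Adding 5 points in controls only gives 45 v 60 and 56.6%. A non-significant any-site result would therefore be weak evidence against the primary finding.

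**The case against.** The strongest reply is that the estimand is already settled. Aim 1 names the Center, two later sections repeat it, and the planning rate comes from the same clinic. On that view the hypothesis has one loose phrase. This stands: the plan does not have two intended primary outcomes.

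A reader might go further and infer that controls are diverted from the Center and that the outcome is biased towards the intervention. The documents do not support this, for four reasons.

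- Central scheduling is not a control-only route. The nurse calls the same line for the intervention arm. The arms differ in who starts the referral and who calls, which is the intervention itself.
- The Viral Hepatitis Clinic sits inside participants' own HIV practice, with a median wait of one week, so it is a natural destination for both arms.
- The Phase 1 text asks both arms about trial referral, so controls are not plainly unsteered.
- The statement that "HCV therapy currently must be managed by a hepatology, gastroenterology, or infectious disease specialist" is a Medicaid reimbursement condition. It does not show that participants obtain HCV care elsewhere.

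The scoring rule is also the same in both arms, and 7 controls against no intervention participants within 60 days is an extreme case that nothing in the documents makes likely.

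Two things survive the reply. Confirmation of trial attendance depends on referral, and the wider claim of linkage to HCV care is not what the primary analysis measures.

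**Conclusion.** The point holds as a matter of definition, ascertainment and interpretation. The hypothesis wording is broader than the outcome, trial attendance is not ascertained in the same way for everyone, and the result supports a statement about attendance at the Viral Hepatitis Center rather than about HCV care in general.

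The size is unknown. The documents give no rate of linkage by other routes and do not show that it differs by arm. The move from p = 0.005 to p = 0.065 is an assumed worst case, and the 10.5–11.4% and 29–32% error rates hold only under the assumed differences between arms. It would be wrong to read 13 points as the true effect, or to conclude that the trial favours the intervention. The planned sample size is unaffected, because it was set on a Viral Hepatitis Clinic rate.

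**What to change.** 1. Keep Viral Hepatitis Center attendance within 60 days as the primary outcome. Use that wording, including attendance rather than enrolment and the site of the trial, in the Aim 1 hypothesis, the Phase 1 definition and the Primary Outcome paragraph.
2. Ascertain trial attendance for every participant in both arms, whether or not a referral was made.
3. Reconcile the Phase 1 text, which on its face has the nurse refer all participants, with Enhanced Usual Care, the opening of Phase 1 and Table 1, where nurse-initiated referral belongs to the intervention arm only.
4. Pre-specify a supportive intention-to-treat analysis with the same z-test, counting any attended HCV-specialist visit or HCV-treating trial visit within 60 days. Take it from the encounter logs, with visit dates. One dated question in the exit interview, asked in both arms, could supplement it.
5. Report the primary result as attendance at the Viral Hepatitis Center, with the any-site result beside it. The supportive analysis should not be a condition for the primary claim, given its incomplete capture and possibly low power.

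The cost is a little more abstraction and one more analysis, largely of data already to be collected. The downside is that care outside Johns Hopkins will be incompletely captured, and exit-interview answers depend on six-month recall.

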### 3. Background

Linkage to HCV care among people co-infected with HIV/HCV is poor. The greatest gap in the United States HCV care cascade begins between diagnosis and linkage to care. Only 25% of PLWH with chronic HCV have attended an HCV appointment, and less than half of those have ever initiated HCV treatment. A large cohort study in Baltimore found that only 21% of injection drug users with HCV had ever seen an HCV specialist. At the Johns Hopkins Moore Clinic, less than half of patients who are referred to an HCV specialist by their primary care provider actually attend the scheduled specialty appointment.

The perceived threat of HCV and perceived need for HCV care among patients is low. This perception, coupled with the fact that HCV is a “silent epidemic”, places PLWH at great risk. Qualitative studies describe that the absence of HCV-related symptoms leads to little interest in receiving HCV treatment. This is exacerbated by a lack of knowledge about HCV and available therapies; horror stories about interferon-related side effects and old ineffective treatments dominate conversations among peers with HCV despite these barriers being minimized with new all-oral therapy. People with HCV also report low motivation to engage in HCV care due to competing demands from work, school or caregiving responsibilities. Therefore, interventions to increase HCV knowledge and motivation, such as education, patient navigation, and appointment reminders are needed to improve linkage to HCV care.

HIV-HCV drug interactions will exist for up to 88% of PLWH. HCV treatment guidelines no longer separate patients with HIV/HCV co-infection from those with HCV only because cure rates are similar in both groups (over 90%). Currently, the only difference in management of HCV in PLWH is the need to manage drug interactions. Patel and colleagues (2015) conducted a cross-sectional study to determine the frequency of contraindicated drug-drug interactions when PLWH are prescribed HCV therapy. Examination of medication lists revealed that the prevalence of interactions was as high as 88.4% depending on the HIV and HCV regimens. Based on these results, it is likely that a large proportion of PLWH who are initiating HCV treatment will have to modify their HIV treatment regimen. Modifying HIV treatment regimens can take months and deter PLWH from starting HCV treatment. A prior study found that HIV combination antiretroviral therapy (ART) modifications can negatively impact quality of life and increase HIV symptom burden. Therefore, new approaches to modifying ART that minimize barriers to HCV treatment initiation are urgently needed to smooth the transition for PLWH.

Interventions that increase perceived need and maximize enabling resources have the potential to improve the HCV care cascade for PLWH. Nurse case management (NCM) components used in similar contexts can be combined to achieve this improvement. Even in the era of interferon, brief HCV education alone significantly increased knowledge and linkage to HCV care by 14-25%. Adding strengths-based NCM and care coordination improves linkage to HIV or HCV care by up to 30%. Reminder systems using text and phone messages are also effective strategies to increase linkage to HIV care and substance use services in combination with other interventions. Finally, the addition of care coordination for ART modification will further participants’ enabling resources and address this important new barrier for PLWH.

